## Subjects:

This is a proposed randomized controlled parallel clinical, prospective split mouth, triple blinded study. Sample size calculation was conducted using G\*Power 3.1.9.4 software based on data obtained from a previous study.[[name]'s paper which compared the effect of different kinematics on post operative pain(patients) ] It was estimated that a minimum sample size of 19 subjects (sides) per group for a total of 38 sides would be essential for an effect size of 0.97 with an alpha error of 0.05 and a power beta of 0.90 to achieve 95% confidence of a true difference between the groups. Sample size was increased by 25% to 25 subjects per group for a total of 50 sides to compensate for drop-outs.

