#### Patient selection and preparation:

All root canal treatments were performed by a single endodontic consultant. All subjects were selected from walk in patients presented to the endodontic clinic of the British university in Egypt. Cases that were diagnosed and did not meet the inclusion criteria were referred to the intern clinic for dental care. Cases that met the inclusion criteria were selected for this study. All patients were verbally informed about the procedure's benefits and that the results of the treatment will be used to this study and the risks of the procedure was explicitly explained to them. After the verbal consent patients were handed a written form consent to sign upon.

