#### Procedure:

Radiographs were taken by a Paralleled long cone periapical radiography. To ensure a visible root canal  $\leq 30^\circ$  of canal curvature and a periapical index (PAI score) of 3–5 according to Orstavik et

al., (1986) in addition of initial confirmation of root canal types. All patients were anesthetized, rubber dam applied, and access cavities were performed. After root canal exploration and scouting, root canal systems were reconfirmed to be the types selected for this study.

Initial binding file was selected for all root canals to ensure it met the inclusion size of mesial roots #20 and distal #30. After patency and glide path were performed by K-files up to size #20, engine driven canal enlargement was applied using E3 Azure files to final finishing size according to the grouping.

Group A: (left side of the patient) will be prepared 2 sizes larger than the IBF, to size 35#/.04 mesial canals and 40#/.04 distal canals.

Group B: (right side of the patient) will be prepared 3 sizes larger than the IBF, to size 40#/.04 mesial canals and 45#/.04 distal canals.

All data of post-operative pain will be recorded by a second blinded clinician through a visual analog scale (VAS). Post-operative monitoring periods will be recorded in 12 hours, 24 hours, 3 days and 1 week.

Data will be sent to the statistician with group names only to fulfill the triple blinding criteria and results will be interpreted

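### Sending the statistician group names only does not secure the triple blinding claimed, because the protocol itself defines A and B by side and size under one fixed rule

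*Protocol*

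**What the plan says.** Under Subjects the Protocol describes the design in one sentence: "This is a proposed randomized controlled parallel clinical, prospective split mouth, triple blinded study". It plans "25 subjects per group for a total of 50 sides to compensate for drop-outs".

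Under Procedure the allocation is fixed for everyone:

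- "Group A: (left side of the patient) will be prepared 2 sizes larger than the IBF"
- "Group B: (right side of the patient) will be prepared 3 sizes larger than the IBF"

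The same section covers two of the people to be kept unaware. For the outcome recorder it says "All data of post-operative pain will be recorded by a second blinded clinician through a visual analog scale (VAS", and gives no means by which that clinician is kept blind. For the analyst it says "Data will be sent to the statistician with group names only to fulfill the triple blinding criteria".

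The operator is a different person from the recorder. Under Patient selection and preparation: "All root canal treatments were performed by a single endodontic consultant". The protocol does not list the three blinded parties. The third is presumably the patient, whose blinding is not questioned here.

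**The concern.** A coded label masks an analyst only while the key to the code is withheld. Here the key is printed in the section that describes the masking step, and the labels are the same ones the protocol uses for the arms. The sentence nevertheless presents the step as what fulfils the triple-blinding requirement.

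The outcome is post-operative pain on a visual analogue scale, which is subjective. An analyst who knows which label is which arm can be swayed, even unintentionally, when choosing among analyses. A recorder who knows the arm might influence how a score is obtained or written down. Because side and arm coincide in every patient, any such influence could run the same way throughout and would not average out. At the least, the report would claim a protection that the described procedure does not provide.

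**Working it through.** The question is one of logic, so the check sets the statements side by side.

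1. **Scope of the rule.** Inclusion criteria refers to 25 patients, each with molars on both sides: 25 × 2 = 50 sides, which agrees with the total under Subjects. Procedure gives no exception to left = A and right = B, so the rule fixes the arm of every side in the study. This count describes coverage and does not measure bias.

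2. **What the labels carry.** Procedure attaches three things to each name:

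| Group name | Side | Finishing size relative to the initial binding file |
|---|---|---|
| A | left | two sizes above |
| B | right | three sizes above |

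Each of name, side and size determines the other two.

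3. **The analyst.** The masking step removes everything except the name. By step 2 the name alone gives the arm to a reader of the protocol. The step therefore protects only an analyst who has not seen the protocol and has not been told the rule. The document describes no neutral recoding, no withheld key and no restriction on who sees the rule.

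4. **The recorder.** If the recorder knows the side of a score, blindness depends wholly on not knowing the rule. Procedure does not say how scores are indexed, so it is not established that the recorder needs the side.

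5. **The effect of random assignment by side.** If side were assigned to arm at random within each patient, side alone would no longer reveal the arm. That holds only while the list is concealed: a list the recorder or analyst can see protects no better than the fixed rule. The protection comes from concealment, and randomisation is what makes concealment possible.

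6. **Agreement with Subjects.** Subjects says the study is randomised, and Procedure assigns by side without any random element. That is a related but separate contradiction, and one of the changes below resolves both.

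**The case against.** The strongest reply is that sending coded group names is ordinary practice and fails only if the statistician holds the protocol or is told the key. Nothing in the document says that happens. This stands, and it limits the finding to unprotected blinding.

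A second reply is that key-holding and release are often set out in an SAP or data-handling document that is not shown, and that the Procedure text ends without a full stop, so more may have followed. This does not remove the point. The protocol is not silent on masking: it names a specific step, says that step meets the requirement, and defines the labels alongside it. A later document could add recoding, but this sentence would still be wrong about what achieves the blinding.

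Three stronger readings are tempting, and the document supports none of them:

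- **Blinding was broken.** A reader might infer this from the printed key. The text does not show that the recorder or statistician knew the rule. It calls the recorder blinded and has someone else perform the treatment.
- **The recorder necessarily knows the side.** Scores could be logged by visit and mapped to side by another person; Procedure leaves this open.
- **The error rate is inflated by a calculable amount.** Any such figure would rest on an assumed arm-related shift by the recorder and on a test the protocol does not name, and it would not describe the analyst step quoted. The Introduction calls pain a patient-related outcome, so the recorder may simply write down the patient's own rating. Nor is it fair to contrast the fixed rule, fully disclosed, with a random list of which one entry is disclosed, since a fully disclosed list reveals just as much. What remains is qualitative: a one-line rule is easier to learn or guess than a list.

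Finally, the text mixes past and future tense, so treatment may be partly or wholly complete. That limits which remedies are still available but leaves the wording problem in place.

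**Conclusion.** The point holds in a limited, qualitative form. As written, the step offered to fulfil triple blinding does not secure it, because the group names are defined by side and size in the same section and identically for every patient. That much follows from the text alone.

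Any actual bias depends on conditions the document does not establish. For the analyst, these are knowledge of the rule and discretion over the analysis. For the recorder, they are knowledge of the rule and of the side, an expectation about the larger size, and some influence on the rating. No numerical magnitude can be given. The change is still worth making, because the outcome is subjective, the claim of triple blinding will be repeated in the report, and the remedy is cheap.

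**What to change.** **All data.** Have an existing staff member who takes no part in scoring or analysis recode the arms to neutral labels (X and Y). Strip the side and anything that reveals it or the finishing size, such as tooth number. Keep the patient identifier so that the two sides of a patient stay linked. Withhold the key until the analysis is locked, and rewrite the masking sentence in Procedure accordingly.

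**Patients not yet treated.** Assign side to arm at random within each patient, from a list concealed from the recorder and the statistician. This also reconciles Procedure with the description of the study as randomised under Subjects.

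**Patients already treated under the fixed rule.** Replace the triple-blind label with a statement of who was kept unaware of the arm and by what means. Recoding can protect the analysis still to come but cannot protect scores already recorded.

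**Cost.** One list, one recoded file with its key, a little time from one person, and wording changes under Subjects and Procedure. The sample size is unaffected. If every patient has already been treated, only the recoding and the wording remain.
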